Procedures. Participants will first be asked questions about their mental health needs, challenges they face accessing care, and strategies they have used to manage their mental health. All participants will then be shown App Store descriptions of ten apps that have received the highest rating by PsyberGuide, a non-profit company that consistently rates existing apps for their safety, data privacy and user ratings. Participants will provide initial impressions on the acceptability and feasibility of using these apps. We will then ask participants if they would be willing to participate in a randomized trial to test these apps, with the aim of recruiting 1000 participants. Participants will be randomized (100 per group) to one of the ten apps. They will be asked to download their assigned app and use it for 4 weeks. We selected four weeks because (1) this is ample time to determine the usability, acceptability and feasibility of these apps (2) based on past remote research, this is when we will see the first effects of apps on mental health outcomes and (3) also based on past research, this is the longest period of time we will be able to maintain a 100-80% of the

sample. After 4 weeks of use, participants will be asked to provide an evaluation of acceptability, feasibility and usability of the app, how often they used the app, and if they found the app helpful. They will also complete PHQ9, GAD7, and brief Difficulties with Emotion Regulation Scale (DERS) and four measures from the IMV model of suicidal behavior – defeat, entrapment, thwarted belongingness, and perceived burdensomeness. The Suicidal Behaviors Questionnaire-Revised (SBQ-R), a four-item self-report that assesses suicide attempts, ideation, communication, and intent since the last assessment. Given some limitations of the attempt item in the SBQ-R (which is combined with suicidal ideation), an additional item "Have you attempted to kill yourself?" will be added. This single-item has been demonstrated to identify a research rated suicide attempt in 89.3% of cases. We will also ask if they used any other mental health apps or services during this 4-week period.

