T-tests and chi-square tests will compare demographic and baseline clinical outcomes by missing data status at follow-up timepoint. Chi-square tests will examine the association between condition assignment and compliance (whether a participant used the app they were assigned to or used an alternative app). All analyses are intent-to-treat. Sensitivity analyses will be conducted excluding those who never downloaded or used the app they were assigned. Analyses of variance will be used to compare conditions on AIM, IAM, and IUS scores at follow-up. A series of mixed effects models using restricted maximum likelihood estimation will be built to test linear time change on the PHQ-9, GAD-7, and DERS-SF, and to test for condition differences at follow-up and change slope. Models will be built in an outwardly nested fashion, such that an initial null model was computed, followed by models that add a random intercept, random time component, condition assignment, and condition x time interaction effects. To test whether there was a dose-response relationship such that the app use frequency was associated with rate of change on PHQ-9, GAD-7, and DERS-SF scores, we will compute another series of mixed effects models for each outcome. An initial model will include variables for time and frequency of use, a second model will add condition terms for each app using Beautiful Mind as reference, a third model will add condition x frequency interaction terms for each app, and the fourth model will include time, frequency, and a time x frequency interaction term. Model comparisons will apply -2 Log Likelihood, Akaike Information Criterion, and Bayesian Information deviance statistics. To test the impact of app use frequency on change over time, similar nested model testing will be applied using an initial null model, followed by models that added dosage, dosage x time interaction, and condition assignment.

Sample Size and Power. A priori power analysis for an ANOVA *F* test indicated that a sample size of 1,000 (n=200 participants in each of the active and control app conditions) would be sufficient with a power of .80 and an alpha of .05 for a minimum detectable effect size (MDES) of Cohen's d=.24 for main effect comparisons between any two conditions.

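### Mixed models are compared on -2LL, AIC and BIC with no deciding criterion; the three can conflict, and some of the planned comparisons are not valid likelihood tests

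*Combined protocol and SAP*

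**What the plan says.** The Analysis section plans three series of mixed models for PHQ-9, GAD-7 and DERS-SF.

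- **Condition series.** Fitted by REML and built up from a null model to condition and then condition x time. This addresses Question 3, which apps improve these outcomes.
- **First dose-response series.** Model 1 has time and frequency of use. Model 2 adds the app terms against a reference app. Model 3 adds condition x frequency. For the last step, "the fourth model will include time, frequency, and a time x frequency interaction term".
- **Second dose series.** Starts from a null model and adds dosage, then dosage x time, then condition.

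The criterion sentence stands between the two dose series: "Model comparisons will apply -2 Log Likelihood, Akaike Information Criterion, and Bayesian Information deviance statistics". The other two series name no different criterion. The section gives no deciding statistic, no threshold or alpha for the deviance difference, no sample size for the BIC penalty and no rule for disagreement. An alpha appears only in the Sample Size and Power paragraph, for an ANOVA: "would be sufficient with a power of .80 and an alpha of .05".

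The number of arms sets the degrees of freedom, and it is stated in two ways. Procedures says "Participants will be randomized (100 per group) to one of the ten apps". The power paragraph has "a sample size of 1,000 (n=200 participants in each of the active and control app conditions", which implies 1,000/200 = 5 arms.

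**The concern.** -2LL at .05, AIC and BIC are three different rules for keeping a term. Each asks the deviance to fall by a different amount, and the gap between them grows with the number of parameters in the term. If none is named in advance, the one to rely on can be chosen after the results are seen. The same data could then be reported as showing a dose-response (AIC) or none (BIC), or as showing app differences (-2LL) or none (BIC).

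There is also a structural problem. A -2LL difference has a chi-square reference only when one model is the other plus extra terms and the two likelihoods are comparable. The step from model 3 to model 4 in the first dose series fails the first condition. REML fits of models with different fixed effects fail the second.

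**Working it through.** **The plan's own figure.** The documents give no error rate for the model comparisons, so there is none to reproduce. The one stated design figure is d = .24. With 200 per arm, the usual two-group formula gives (1.960 + 0.842) x sqrt(2/200) = 0.280 two-sided, or (1.645 + 0.842) x sqrt(2/200) = 0.249 one-sided. That mismatch is a separate matter; only the arm count matters here.

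**Inputs.** 1,000 randomised (Procedures). Ten arms give 10 - 1 = 9 df for condition x time; five arms give 5 - 1 = 4 df. Alpha .05 is borrowed from the power paragraph. Assumptions: ML fits; linear time; frequency as one numeric variable, so time x frequency has 1 df; one baseline and one 4-week assessment, so up to 2,000 rows. The BIC sample size is unstated, so 1,000 (people) and 2,000 (rows) are both shown.

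**Rule.** A term with k df is adopted if the deviance falls by more than the chi-square 95% point on k df (-2LL), 2k (AIC) or k x ln(n) (BIC).

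| Term | -2LL at .05 | AIC | BIC, n = 1,000 to 2,000 |
|---|---|---|---|
| time x frequency, 1 df | 3.84 | 2 | 6.91 to 7.60 |
| condition x time, 4 df | 9.49 | 8 | 27.6 to 30.4 |
| condition x time, 9 df | 16.92 | 18 | 62.2 to 68.4 |

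**Adoption with no true effect** is the chi-square tail area beyond each threshold.

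| Term | -2LL | AIC | BIC |
|---|---|---|---|
| 1 df | 5% | 15.7% | 0.6-0.9% |
| 4 df | 5% | 9.2% | 0.0004-0.0015% |
| 9 df | 5% | 3.5% | below one in a billion |

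**Adoption with a real effect that -2LL finds 80% of the time** is the noncentral chi-square tail, with noncentrality 7.85 (1 df), 11.94 (4 df) and 15.65 (9 df).

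| Term | -2LL | AIC | BIC |
|---|---|---|---|
| 1 df | 80% | 92% | 52-57% |
| 4 df | 80% | 87% | 4-7% |
| 9 df | 80% | 76% | 0.01-0.06% |

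For a real effect of that size, AIC and BIC disagree in 35-40% of trials for the 1-df term. For the app block, -2LL and BIC disagree in 73-76% (4 df) or about 80% (9 df). Taking n = 800 for BIC (80% retention) moves its 1-df null rate to 0.97% and its adoption of a real effect to 8.7% (4 df) or just under 0.1% (9 df), which changes nothing of substance.

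**Nesting.** With ten arms and the intercept left out, model 3 has 1 + 1 + 9 + 9 = 20 fixed effects (time, frequency, condition, condition x frequency). Model 4 has 3 (time, frequency, time x frequency). Model 4 adds one term and drops 18, so neither model contains the other. The same holds against model 2. Model 4 does contain model 1 and differs from it by one term, so that pair gives a proper 1-df test. The plan does not name it.

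**REML.** The REML criterion includes a term that depends on the fixed-effects design matrix. Adding a fixed effect changes that term, and the change depends on the units of the added variable. In a null simulation the REML deviance difference did shift with the units of the frequency variable. The rates above therefore describe ML fits, not REML likelihoods compared as the plan is written.

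**The case against.** Listing the three statistics together is common and is not in itself an error. The plan never says that they decide anything. It says the models will test condition differences in level and slope, and it codes apps against a reference, which fits coefficient tests. If AIC and BIC only describe fit, the rates above are not the trial's error rates. This stands: the rates are conditional on model comparison being the decision rule. It also means one more choice is left open.

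A reader might infer that the criteria contradict each other as a matter of course, with false-positive rates of up to 16% on the trial's main question. The documents do not support that. Conflict needs a deviance drop between the thresholds; with no effect all three agree in about 85% (1 df), 91% (4 df) or 95% (9 df) of trials. The 16% belongs only to the 1-df dose term, and dose-response is not among Questions 1 to 3. For condition x time with ten arms, AIC is slightly stricter than the 5% test.

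A reader might also infer that the plan offers no valid route to the dose-response question. That goes too far. The second dose series adds dosage x time as its own step, which is close to what is needed, and nothing says model 4 must be tested against model 3. What remains is that the plan has two routes to one question and does not say which one answers it.

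**Conclusion.** The point holds as a gap in the decision rule, with a faulty comparison inside it. No deciding statistic is named, and the choice matters. For time x frequency, the null adoption rate is 5%, 15.7% or 0.6-0.9%. For condition x time the main difference is in power: BIC would almost never adopt an app effect that -2LL finds 80% of the time, whether the trial has ten arms (under 0.1%) or five (4-7%). Separately, the step from model 3 to model 4 is not a likelihood-ratio test, and REML likelihoods cannot be used to compare fixed effects.

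The sizes rest on ML fits, a single numeric frequency variable, two assessments, and the named criterion being what decides. They do not show that the trial's error rate will be 16%, nor that app differences will be missed; either would need a rule that the plan does not state. The change should be made before the data are analysed.

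**What to change.** Add to the Analysis section one deciding test per question, at .05, on ML fits:

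- **App differences in change:** the likelihood-ratio test of the whole condition x time block, with df equal to the number of arms minus 1. The arm count must first be reconciled between Procedures and the power paragraph.
- **Dose-response:** the 1-df likelihood-ratio test of time x frequency between two models that differ only by that term. Use either model 4 against model 1, or the term added to model 3. State which of the two dose series is the one that answers the question.

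Report AIC and BIC as description only.

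The cost is one or two sentences and ML fits for the comparisons. Data collection and sample size do not change.

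### The dosage x time test does not adjust the slope for baseline severity, so regression to the mean can appear as, or hide, an effect of app use that the plan calls impact

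*Combined protocol and SAP*

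**What the plan says.** Under Procedures, the randomised factor is the app: "Participants will be randomized (100 per group) to one of the ten apps". After 4 weeks participants are asked "how often they used the app". No other source of use data is described, so the dose variable is self-chosen and self-reported once, at the same visit as the outcomes.

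The Analysis section then plans two series of mixed models on PHQ-9, GAD-7 and DERS-SF.

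- The first has the stated aim "To test whether there was a dose-response relationship such that the app use frequency was associated with rate of change". Its steps begin "An initial model will include variables for time and frequency of use, a second model will add condition terms for each app", continue with condition x frequency terms, and end where "the fourth model will include time, frequency, and a time x frequency interaction term".
- The second is introduced with "To test the impact of app use frequency on change over time, similar nested model testing will be applied", starting from a null model followed by "models that added dosage, dosage x time interaction, and condition assignment".

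Neither list contains a baseline-severity covariate, a baseline x time term or any other confounder. The baseline score enters only as the time-0 outcome. The same section compares baseline clinical outcomes by missing-data status, so the scores needed for adjustment will exist.

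**The concern.** Randomisation does not protect a comparison of heavy with light users, and labelling all analyses intent-to-treat does not change that. Someone who enrols in a bad week scores high, may open the app more because of that week, and will on average score lower four weeks later whether or not the app does anything. Across the sample this produces a negative dosage x time coefficient with no effect of use. If people in a bad week use the app less, the bias runs the other way and can hide a real effect.

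The second series is worded causally, and the findings are to be passed quickly to suicide-prevention organisations and other partners. A statement about the impact of use would reach readers who cannot see that the contrast was not randomised.

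**Working it through.** **Inputs from the document.** One baseline and one follow-up at 4 weeks; 1,000 randomised; expected retention of 80 to 100%, so at least .80 x 1,000 = 800 completers. The only power figure (d = .24) concerns comparisons between two conditions. No figure is given for the dosage models, so there is none to reproduce here.

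**Inputs assumed.** The baseline/follow-up correlation rho (.5 to .7) and the frequency/baseline correlation c (.1 to .3) are not in the document. Scores and frequency are in SD units, the true effect of use is zero, and the test is two-sided at 5%.

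**Step 1: what the planned term estimates.** Frequency F is known only for people with week-4 data. With two timepoints per person, the time x F coefficient is the slope of (Y1 - Y0) on F. A REML random-intercept fit on one simulated dataset gave -0.093 (SE 0.030) for time x F, and least squares on the change score gave the same two numbers. In general:

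slope = corr(F,Y1) - corr(F,Y0)

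**Step 2: use follows the observed baseline score.** Then corr(F,Y1) = rho x c, and

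slope = -c(1 - rho) = -.2 x .4 = -0.08 SD per SD of use, at rho = .6 and c = .2

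SE = sqrt(2(1 - rho)) / sqrt(N) = sqrt(.8) / sqrt(800) = 0.032

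The ratio is about -2.5, so rejection is frequent although use does nothing. Simulated false rejection of the planned test, N = 800:

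| rho | c = .1 | c = .2 | c = .3 |
|---|---|---|---|
| .5 | 30% | 81% | 99% |
| .6 | 26% | 71% | 97% |
| .7 | 20% | 59% | 91% |

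At rho = .6 and c = .2, full retention (N = 1,000) raises 71% to 80%. With c = -.2 the slope reverses to +0.08 and is rejected in 70% of runs. Regressing week-4 score on F and baseline score gives a slope of about 0.00 and rejection of 4 to 5% in every cell of this table.

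**Step 3: use follows stable severity only.** Then corr(F,Y1) = corr(F,Y0), so the planned slope is zero; the frequency main effect absorbs the difference in level. Simulated rejection is 4 to 6%. Here it is the baseline-adjusted model that is biased:

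adjusted slope = c(1 - rho) / (1 - c^2) = .2 x .4 / .96 = +0.083 SD at rho = .6 and c = .2

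It falsely rejects in 82% of null trials. The sign is opposite to that in step 2: more use looks harmful.

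**Step 4: a mixture.** With an even mix of the two mechanisms at rho = .6 and c = .2, the planned test falsely rejects in 24% of runs.

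**Step 5: use follows improvement.** Suppose use does nothing but correlates .1 with unexplained improvement, because people who feel better keep going or recall more use. At rho = .6 and N = 800, the planned and baseline-adjusted estimates were both significant in the same direction in 67 to 70% of null trials (two separate runs), and in over 99% when that correlation was .2.

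**The case against.** The strongest reply is that greater use by sicker people is not enough to bias the planned test. That stands. A reader might infer from the missing covariate that any severity/use correlation distorts the slope; step 3 shows that it does not. Only the part of the baseline score that will not persist matters. Nor is baseline absent from the models, since it is the time-0 outcome; what is missing is adjustment of the slope.

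A second tempting inference is that adding the baseline score repairs the analysis. It does so only under the mechanism in step 2. A third is that agreement between the two models establishes a dose-response. Requiring agreement does guard against the selection mechanisms in steps 2 to 4, where joint false claims stayed at or below 3.2%, but it fails against reverse causation or recall, as step 5 shows.

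It is also fair to say that the first series is worded as association and *impact* appears only for the second; that dose-response is not among Questions 1 to 3; and that the document predicts no finding about use and says nothing about advising more of it. These points limit the weight of the concern. They do not remove it: the plan neither states nor checks the stable-severity assumption on which its test depends, and causal wording remains for a non-randomised exposure.

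**Conclusion.** The concern holds in a limited form. The planned dosage x time test is the regression of change on self-chosen use, and it is valid as a test of no association with change beyond regression to the mean only if use is unrelated to the transient part of the baseline score. Over the assumed correlations, with 800 completers and no true effect, its false rejection rate lies anywhere from about 5% (stable severity only) to about 99% (observed score, rho = .5, c = .3). The 71% at .6 and .2 is an illustration, not a prediction. The document gives neither correlation, nor the sign of the second, nor the mechanism, so the size and direction of any bias in this trial are unknown. Neither model supports a causal conclusion. This is a secondary analysis, and the change is worth making because it costs little.

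**What to change.** - Keep the planned dosage models.
- For each of PHQ-9, GAD-7 and DERS-SF, add a sensitivity model of week-4 score on use frequency, with baseline score and condition as covariates.
- Tabulate baseline severity by level of use, so that readers can see whether and how use relates to starting score.
- Report both estimates with intervals. State in advance that disagreement gives no support for a dose-response and that agreement is not proof of one, because neither model deals with reverse causation or week-4 recall.
- Replace *impact* with *association* in the plan and in everything disseminated.

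The cost is one extra regression per outcome on data already collected, one table, and a weaker permitted claim about use.

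### The power statement assumes 200 per condition (five arms), but the plan randomises ten apps at 100 each; at 100 per arm, d = .24 has about 40% power, not 80%

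*Combined protocol and SAP*

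**What the plan says.** In Methods, Procedures, the plan invites survey participants into the trial "with the aim of recruiting 1000 participants" and then states "Participants will be randomized (100 per group) to one of the ten apps". Ten apps at 100 each account for the full 1,000. No control app is named there. The same section justifies the four-week period partly on retention: "this is the longest period of time we will be able to maintain a 100-80% of the" sample.

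In Analysis, Sample Size and Power, the calculation is described as an ANOVA F test with power .80 and alpha .05, based on "a sample size of 1,000 (n=200 participants in each of the active and control app conditions". The resulting minimum detectable effect size (MDES), Cohen's d = .24, is said to be "for main effect comparisons between any two conditions". Sidedness, covariates, a baseline–follow-up correlation, dropout and multiplicity are not mentioned.

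Elsewhere in Analysis, the only ANOVA specified is "Analyses of variance will be used to compare conditions on AIM, IAM, and IUS scores at follow-up". For the dose-response models, "a second model will add condition terms for each app using Beautiful Mind as reference". That app is a reference category; the plan does not call it the control.

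**The concern.** The same 1,000 participants are divided in two incompatible ways, and the MDES is attached to the larger arm size. No section describes a five-condition design or a pooling of apps that would turn ten arms of 100 into five groups of 200.

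The MDES is the only statement in the plan of how small a difference between two apps the trial can find. The trial's questions are which apps are acceptable, feasible and usable and which improve symptoms, and the answers are to be disseminated quickly. A reader who relies on .24 could take a non-significant comparison of two apps as evidence that they differ by less than that. The point concerns comparisons between apps; the stated MDES does not address change within an app.

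**Working it through.** **Inputs.** From Sample Size and Power: N = 1,000; 200 per condition; power .80; alpha .05; d = .24 for any two conditions. From Procedures: ten apps, 100 per group, retention 80–100%. Assumed because not stated: two-sided test, no covariate, no multiplicity correction.

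**Arm count.** 1,000 / 200 = 5 conditions. Against this, 10 × 100 = 1,000.

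**Formulas** (SD = 1, n per arm, normal approximation):
- Power ≈ Φ(d·√(n/2) − 1.960)
- MDES at 80% power ≈ (1.960 + 0.842)·√(2/n)

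**The plan's own figure, n = 200.** 0.24 × √100 = 2.400; Φ(0.440) = 0.670. MDES = 2.802 × √0.01 = 0.280. The stated 80% at .24 is not reproduced; it would need 273 per arm.

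**The design as randomised, n = 100.** 0.24 × √50 = 1.697; Φ(−0.263) = 0.396. MDES = 2.802 × √0.02 = 0.396.

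**With 20% loss.** From 100 to 80: 0.24 × √40 = 1.518; Φ(−0.442) = 0.329; MDES 0.443. From 200 to 160: 0.24 × √80 = 2.147; Φ(0.187) = 0.574; MDES 0.313.

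The noncentral t with error degrees of freedom pooled over all arms gives nearly the same results:

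| Design | n per arm | Power at d = .24 | MDES |
|---|---|---|---|
| Five arms | 200 | 66.9% | .280 |
| Five arms, 80% retained | 160 | 57.3% | .314 |
| Ten arms | 100 | 39.6% | .397 |
| Ten arms, 80% retained | 80 | 32.9% | .444 |

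**Could an unstated assumption explain .24?**
- *One-sided test (normal approximation):* at n = 200, power 77.5% and MDES .249; at n = 100, 52.1% and .352.
- *Baseline adjustment with correlation r* (variance factor 1 − r²): an assumed r = .5 gives a factor of .75, so MDES .243 at n = 200, .344 at n = 100 and .384 at n = 80. For r from .3 to .7 the MDES runs from .268 to .200 at n = 200, .378 to .283 at n = 100, and .423 to .317 at n = 80. Reaching .24 needs r of about .52 at n = 200, .80 at n = 100 and .84 at n = 80.
- *Main effect averaged over two time points* (variance factor (1 + r)/2): n = 200 reaches .24 at r of about .465. At n = 100 the MDES is .280 even at r = 0, and .24 would need r of about −.27.
- *Omnibus F with d taken as 2f:* N = 1,000 gives .219 for five groups and .251 for ten.

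The first three do not bring n = 100 to .24 unless the baseline correlation is about .80. The omnibus figure is not a difference between two conditions.

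**The case against.** The strongest reply is that the 40% combines the arm size in Procedures with the effect size in Sample Size and Power. The plan claims 80% only at 200 per condition, and nothing shows which section is current. If five arms of 200 is the true design, the gap is smaller: 67% against 80%, or .28 against .24. That is right, and the 40% is therefore conditional on the ten-arm design. The contradiction remains either way, and so does the failure to reproduce the stated figure under the stated inputs.

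Sidedness is not stated, and a one-sided test at n = 200 comes close (MDES .249). However, an ANOVA F test of two groups is equivalent to a two-sided t test, and the one-sided reading at 100 per arm still gives only 52%.

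The plan names an F test, and omnibus effect sizes fall near .24: .219 to .245 for five groups and .251 to .281 for ten, as N goes from 1,000 to 800. An omnibus value relabelled as pairwise is a possible origin of the figure. It does not support the claim, which is about any two conditions.

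A correlation of about .5 is another possible origin at n = 200. It is not stated, and it does not fit the follow-up-only ANOVA on the acceptability, feasibility and usability scores, which has no baseline term.

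Two limits on the numbers stand. Eighty per arm applies to the follow-up ANOVA; the mixed models for PHQ-9, GAD-7 and DERS-SF can retain participants who have baseline data only. The figures also carry no multiplicity correction. Ten apps give 45 pairs, and Bonferroni over all of them would raise the MDES at 100 per arm to (3.261 + 0.842) × √0.02 = .58.

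**Conclusion.** The concern holds. The plan gives two incompatible arm counts, and its MDES does not describe the trial it randomises. With ten arms of 100, power at d = .24 is about 40% (33% at 80 per arm) and the MDES is about .40 (.44). With five arms of 200, power is 67% and the MDES .28. These figures assume a two-sided .05 pairwise test with no covariate and no multiplicity correction. A one-sided test or an assumed correlation of .5 narrows the shortfall at 100 per arm (MDES .35 and .34) without closing it. The source of .24 cannot be determined from the documents. This should be corrected before the figure is relied on.

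**What to change.** Make the number of arms and the number per arm agree between Procedures and Sample Size and Power, and say which app, if any, is the control. Then replace d = .24 with the MDES for the design actually randomised:

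- *Ten arms:* With 100 randomised per app, a comparison of any two apps has 80% power at two-sided .05, without covariate or multiplicity adjustment, for d of about .40; for the follow-up ANOVA with 80 per app analysed, d of about .44.
- *Five arms of 200:* correct Procedures, and state either .28 or the correlation that produces .24.
- *If the calculation was baseline-adjusted or repeated-measures:* state the assumed correlation and the outcomes it applies to, and recompute for the actual arms. With ten arms, r = .5 gives .34 at 100 per arm and .38 at 80.

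The cost is protocol and SAP wording only. The stated MDES becomes less favourable; no additional enrolment is requested.

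### The claim of .80 power at d = .24 for any pair of conditions holds neither for a two-sided pairwise contrast nor, in general, for the omnibus F test

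*Combined protocol and SAP*

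**What the plan says.** The power paragraph names its basis: "A priori power analysis for an ANOVA *F* test indicated that a sample size of 1,000" (with "n=200 participants in each of the active and control app conditions") is "sufficient with a power of .80 and an alpha of .05". The detectable effect is then given as a "minimum detectable effect size (MDES) of Cohen's d=.24 for main effect comparisons between any two conditions". At 1,000 participants, 200 per condition implies five conditions.

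The Procedures section has the same total, "with the aim of recruiting 1000 participants", but a different layout: "Participants will be randomized (100 per group) to one of the ten apps".

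For the rating scores the Analysis section says "Analyses of variance will be used to compare conditions on AIM, IAM, and IUS scores at follow-up". It names no pairwise contrast, post hoc test or multiplicity rule for them. Neither section gives the sidedness of the test or the pattern of means behind the power calculation. The power paragraph makes no allowance for dropout, although the Procedures section expects to keep 80 to 100% of the sample to week 4.

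**The concern.** The sentence joins two different quantities. A Cohen's d between two conditions is the effect size of a contrast with 1 degree of freedom. An ANOVA across all conditions is an omnibus test with 4 degrees of freedom (five conditions) or 9 (ten). Its power depends on the spread of all the means, so a single pairwise d does not determine it.

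The ANOVAs are the only test named for Question 1, on which apps are acceptable, feasible and usable, and the findings are to be disseminated quickly to suicide-prevention organizations. Anyone who takes the power sentence at face value could read a non-significant F as showing that no two apps differ by as much as d = .24. The design does not give that assurance.

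**Working it through.** **Inputs.** N = 1,000, alpha .05, power .80, d = .24 and 200 per condition come from the power paragraph. Ten groups of 100 and 80 to 100% retention come from the Procedures section. Assumed: two-sided test, equal SDs (set to 1), no multiplicity adjustment.

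**Step 1: the stated figure as a pairwise contrast.** Power = Φ(d/√(2/n) − 1.96); detectable d = (1.96 + 0.84)·√(2/n).

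- n = 200: .24/√(2/200) = 2.40, power Φ(0.44) = .67; detectable d = 2.80 × .100 = .28. Reaching .80 at d = .24 needs 273 per arm.
- n = 100: .24/√(2/100) = 1.70, power Φ(−0.26) = .40; detectable d = 2.80 × .141 = .40.
- One-sided at n = 200: power .775, detectable d = .249. This is close, but it does not reach .80.

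The stated .24 is not reproduced.

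**Step 2: the omnibus F at a largest difference of d = .24.** Noncentral F with k − 1 and N − k degrees of freedom. The noncentrality λ depends on the pattern of the k means:

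- two apps differ, rest midway: λ = n·d²/2
- evenly spaced: λ = n·d²·k(k+1)/[12(k−1)]
- one app against the rest: λ = n·d²·(k−1)/k
- split at the extremes (a apps and b apps): λ = n·d²·ab/k

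Here n·d² is 200 × .0576 = 11.52 for five arms and 100 × .0576 = 5.76 for ten.

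| Pattern | 5 × 200: λ | power | 10 × 100: λ | power |
|---|---|---|---|---|
| Two differ, rest midway | 5.76 | .45 | 2.88 | .17 |
| Evenly spaced | 7.20 | .55 | 5.87 | .33 |
| One against the rest | 9.22 | .67 | 5.18 | .29 |
| Split (2 v 3; 5 v 5) | 13.82 | .86 | 14.40 | .75 |

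**Step 3: the effect detectable with .80 power.** Find the λ that gives .80, take f = √(λ/N), and convert to d by inverting the formulas above. For example, for ten arms of 100, λ = 15.78, f = √(15.78/1000) = .126, and d with the rest midway = √(2 × 15.78/100) = .56. The 80% retention rows use 160 and 80 per arm.

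| Layout | λ | f | d, rest midway | d, one against the rest | Pairwise d, unadjusted |
|---|---|---|---|---|---|
| 5 × 200 | 11.99 | .110 | .35 | .27 | .28 |
| 5 × 160 | 12.01 | .123 | .39 | .31 | .31 |
| 10 × 100 | 15.78 | .126 | .56 | .42 | .40 |
| 10 × 80 | 15.82 | .141 | .63 | .47 | .44 |

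**Step 4: other routes to .24.** Two come close. A repeated-measures main effect with two groups of 200, two time points and correlation .5 has power .79. A five-condition omnibus F with 160 per arm and d read as 2f (f = .12, λ = 800 × .0144 = 11.52) has power .78. Each needs inputs that the plan does not state.

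**The case against.** The strongest defence is that the documents nowhere use the word omnibus. A comparison of two conditions inside an ANOVA is itself an F test with 1 degree of freedom, so the sentence may simply mean pairwise comparisons. That is a fair reading, and the omnibus reading of the rating analysis, though natural, is inferred. It does not rescue the figure, because the pairwise test has power .67 at 200 per arm.

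A second defence is that the sentence is never tied to the rating scores. It may size the repeated PHQ-9, GAD-7 and DERS-SF outcomes, or may be an omnibus f relabelled as d after allowing for dropout. Step 4 shows that both are possible. Neither can be confirmed, so how .24 was obtained remains open.

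A reader might also infer more than the documents support:

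- *That omnibus power is always far below .80, or that the F test would miss d = .24 most of the time.* At five arms of 200 it misses more often than not in one of the four patterns, and in another its power is .86.
- *That the pairwise contrast is correctly sized and only the change of test causes the shortfall.* The contrast is itself short. With one app against the rest at 5 × 200, the omnibus F has about the same power (.67), and with the split pattern it has more.
- *That the low ten-arm figures come only from the type of test.* Much of that drop reflects 100 rather than 200 per group; pairwise power there is already .40.
- *That the sponsor intends to call the apps interchangeable after a null F.* Nothing in the plan says so. The risk lies in how the power sentence could be read.

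**Conclusion.** The point holds in this limited form. A claim about any two conditions has to survive the least favourable arrangement of the other means, and there omnibus power is .45 at 5 × 200 and .17 at 10 × 100. No pattern examined reaches .80 with ten arms of 100, and only the split pattern does with five of 200. The pairwise reading fails at both sizes. Settling the arm count would therefore not make the sentence correct.

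These results assume a two-sided alpha of .05, equal variances, full retention and no multiplicity adjustment. Dropout or an adjustment for many pairs would lower them further. The defect lies in a stated design property, not in the planned analysis itself, and should be corrected before results are interpreted against it.

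**What to change.** 1. Reconcile 200 per condition (five conditions) with 100 per group (ten apps).
2. State whether the powered test is the omnibus F or a named pairwise contrast, for which outcome, with what sidedness and multiplicity rule. If all pairs are to be tested with a Bonferroni correction, the detectable d at full retention becomes .36 (10 pairs, 200 per arm) or .58 (45 pairs, 100 per arm).
3. Replace the claim of .80 power at d = .24 with the row of the Step 3 table that matches the reconciled layout. For an omnibus test, give f and the assumed pattern of means beside any d. For a contrast, give the pairwise figure.
4. Give the 80% retention row as well.
5. Add a sentence that a non-significant omnibus F does not exclude a difference of d = .24 between two apps.

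The cost is a rewritten power paragraph. No participants or assessments are added. The downside is a larger, less favourable stated detectable effect.
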